CRITERIA FOR TREATMENT CONTINUATION	
Further treatment cycles (i.e., Cycle 2 or subsequent) will be administered every three weeks (PM01183 or topotecan) or every four weeks (PLD) (with a window of \pm 48 hours in all of them) if the patient fulfills all the re-treatment criteria defined in Table 2 (PM01183), Table 3 (PLD) or Table 4 (topotecan).
 
Table 2. Criteria for treatment continuation with PM01183 (Arm A).
 
  
 Variable	Day 1	
   
 ECOG PS	≤ 2	
 
 ANC	$\geq 1.5 \times 10^9/l$	
 
 Platelets	$\geq 100 \times 10^9/l$	
 
 Hemoglobin ^a	$\geq 8 \text{ g/dl}$	
 
 Total bilirubin	$\leq 1.5 \times \text{ULN}$ or direct bilirubin $\leq \text{ULN}$ if total bilirubin $> \text{ULN}$	
 
 Albumin	$\geq 2.7 \text{ g/dl}$	
 
 AST/ALT	$\leq 3.0 \times \text{ULN}$	
 
 CPK	$\leq 2.5 \times \text{ULN}$	
 
 Calculated CrCl (Cockcroft and Gault's formula)	$\geq 30 \text{ ml/min}$	
  
	Variable	Day 1	ECOG PS	≤ 2	ANC	$\geq 1.5 \times 10^9/l$	Platelets	$\geq 100 \times 10^9/l$	Hemoglobin ^a	$\geq 8 \text{ g/dl}$	Total bilirubin	$\leq 1.5 \times \text{ULN}$ or direct bilirubin $\leq \text{ULN}$ if total bilirubin $> \text{ULN}$	Albumin	$\geq 2.7 \text{ g/dl}$	AST/ALT	$\leq 3.0 \times \text{ULN}$	CPK	$\leq 2.5 \times \text{ULN}$	Calculated CrCl (Cockcroft and Gault's formula)	$\geq 30 \text{ ml/min}$
Variable	Day 1																				
ECOG PS	≤ 2																				
ANC	$\geq 1.5 \times 10^9/l$																				
Platelets	$\geq 100 \times 10^9/l$																				
Hemoglobin ^a	$\geq 8 \text{ g/dl}$																				
Total bilirubin	$\leq 1.5 \times \text{ULN}$ or direct bilirubin $\leq \text{ULN}$ if total bilirubin $> \text{ULN}$																				
Albumin	$\geq 2.7 \text{ g/dl}$																				
AST/ALT	$\leq 3.0 \times \text{ULN}$																				
CPK	$\leq 2.5 \times \text{ULN}$																				
Calculated CrCl (Cockcroft and Gault's formula)	$\geq 30 \text{ ml/min}$																				

Other non-hematological drug-related AEs (except isolated increased GGT and/or AP; grade 2 alopecia, constipation, fatigue, neuropathy, and not optimally treated nausea)	Grade \leq 1																		

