SAFETY EVALUATIONS	
Patients will be evaluable for safety if they have received any partial or complete treatment infusion.
 
All AEs will be graded according to the NCI-CTCAE v.4.
 
Treatment delays, dose reduction requirements and reason for treatment discontinuation will be monitored throughout the study.
 
The safety profile of patients will be monitored throughout the treatment and up to 30 days after the last treatment infusion (end of treatment, EOT), or until the patient starts a new antitumor therapy or until the date of death, whichever occurs first.
 
Any treatment-related AEs will be followed until recovery to at least grade 1 or stabilization of symptoms, whichever occurs first.

	
An interim safety analysis will be performed by the IDMC after the recruitment of the first 40 patients in the PM01183 arm (Arm A) to assess if the addition of primary CSF prophylaxis might be necessary. Although febrile neutropenia did not occur in the first-in-human PM01183 single-agent study, according to pooled data available from all ongoing phase II studies at 7.0 mg flat dose (FD), it occurred in about 16% of patients. In this clinical trial, the expected percentage of febrile neutropenia is lower, as the PM01183 dose will be administered based on BSA and with a dose (3.2 mg/m²) below the RD found in the first-in-human PM01183 trial (4.0 mg/m² = 7.0 mg FD).
 
Furthermore, PM01183, PLD and topotecan dose will be capped at a BSA of 2.0 m² in those patients who have a greater BSA.
 
At the time of the interim safety analysis, recruitment in the control arm (Arm B, PLD and topotecan) is also expected to be 40 patients.
 
Safety evaluations will be also performed by the IDMC during the futility analysis to be conducted in the two treatment arms once 210 patients are recruited (i.e., ~105 patients enrolled in each arm).
															
PATIENT-REPORTED OUTCOMES (PRO)	
PRO will be assessed every eight weeks from randomization and while on treatment to determine if efficacy and side effects are accompanied by measurable changes in the quality of life of patients. EORTC QLQ-C30 and EORTC QLQ-OV28 questionnaires will be used.
															

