5.4 PRE-TREATMENT ASSESSMENTS

During the pre-treatment period, following signature of the ICF, the Investigator will confirm the patient's eligibility for the study by conducting the assessments summarized in [Table 5](#).

Table 5. Screening period: pre-treatment assessments.

	ASSESSMENT	TIME
1. Written informed consent (general and pharmacogenetic and PGx sub-study)		Before any study procedures.
2. Medical and cancer history/ clinical examination	♦ Demographic data.	Within 28 days prior to first infusion.
	♦ Medical and cancer history/baseline condition: 
 ◦ Primary diagnosis. ◦ Prior treatments (with best response and TTP, when available). ◦ Documented date of relapse. ♦ Disease-related signs and symptoms. ♦ Complete physical examination, including weight, height and calculation of BSA. ♦ Concomitant therapies. 	Within 14 days prior to first infusion.*/**
	♦ Performance status (ECOG PS).	Within 7 days prior to first infusion.*
	♦ Vital signs: heart rate, blood pressure and body temperature.	
3. Laboratory tests	♦ Hematology: differential WBC counts (including neutrophil, lymphocyte and monocyte counts), platelet count and hemoglobin. ♦ Biochemistry: Liver function test (ALT, AST, AP, GGT, total bilirubin; direct bilirubin only if total bilirubin is abnormally high); total proteins, albumin, creatinine, CPK, glucose, calculated CrCL (as per Cockcroft and Gault's formula), and serum electrolytes (Na ⁺ , K ⁺ , Cl ⁻).	Within 7 days prior to first infusion.***
4. Pregnancy test (if women of childbearing potential)	Assessment of β-hCG (urine or serum).	Within 7 days prior to first infusion, if applicable.***
5. ECG	Cardiac rhythm will be identified in ECG intervals of at least 30 seconds of duration, PR interval, QT interval (raw), heart rate and QRS complex.	Within 7 days prior to first infusion.***
6. LVEF	ECHO or MUGA.	Within 14 days prior to first infusion.****
7. PGx	Available stored paraffin-embedded tumor tissue samples; only in those patients that give their written informed consent for the PGx sub-study.	-

	ASSESSMENT	TIME
8. Radiological tumor assessment	Contrast enhanced helical CT-scan or MRI, as clinically relevant.	Within 14 days prior to first infusion.***
9. Tumor marker evaluation	CA-125.	Within 7 days prior to first infusion.***
10. Patient-reported outcomes	EORTC QLQ-C30 and EORTC QLQ-OV28 questionnaires.	Within 7 days prior to first infusion.*

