7. Pharmacogenetics	Only in those patients that give their written informed consent for the pharmacogenetic sub-study	One blood sample will be collected before treatment start in patients treated in Arm A along with the first pharmacokinetic sample of Cycle 1 for the pharmacogenetic sub-study.
8. Radiological tumor assessment	Contrast enhanced helical CT-scan or MRI, as clinically relevant.	Every eight weeks from randomization until evidence of PD.*

	ASSESSMENT	TIME
9. Tumor marker evaluation	CA-125.	Every eight weeks from randomization until evidence of PD, but only if baseline levels were higher than normal.*
10. Patient-reported outcomes	EORTC QLQ-C30 and EORTC QLQ-OV28 questionnaires.	Every eight weeks from randomization.*
11. Adverse events	As per NCI-CTCAE v.4.	Throughout the “on treatment” period.**

Regardless of the treatment administered, the same schedule of assessments will apply.

* A 3-day window will be allowed for laboratory tests and ECG, a 1-week window for tumor assessments as per RECIST v.1.1, tumor marker evaluation and patient-reported outcomes, and a 1-day window for clinical assessments (ECOG PS, vital signs, weight, BSA, etc.).

** “On treatment period” = from first infusion of the study treatment (PM01183, PLD or topotecan) to EOT [30 days after the day of the last dose administration, unless the patient starts a new antitumor therapy or dies (whichever occurs first), in which case the date of administration of this new therapy or the date of death will be considered the date of end of treatment].

AE, adverse event; ALT, alanine aminotransferase; AP, alkaline phosphatase; AST, aspartate aminotransferase; β -hCG, beta subunit of human chorionic gonadotropin; BSA, body surface area; CPK, creatine phosphokinase; CrCL, creatinine clearance; CT, computed tomography; ECG, electrocardiogram; ECHO, echocardiography; ECOG, Eastern Cooperative Oncology Group; EOT, end of treatment; EORTC, European Organization for Research and Treatment of Cancer; GGT, gamma glutamyltransferase; LVEF, left ventricular ejection fraction; MRI, magnetic resonance imaging; MUGA, multiple-gated acquisition scan; NCI-CTCAE, National Cancer Institute Common Terminology Criteria for Adverse Events; PLD, pegylated liposomal doxorubicin; PS, performance status; RECIST, Response Evaluation Criteria in Solid Tumors, WBC, white blood cells.

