6.3 STARTING DOSES AND SCHEDULE

6.3.1.1 Experimental Arm (PM01183): Arm A

- 3.2 mg/m^2 on Day 1 q3wk (three weeks = one treatment cycle)

Dose will be rounded to the first decimal.

6.3.1.2 *Control Arm (PLD and topotecan): Arm B*

- **PLD starting dose and schedule:**

50 mg/m² on Day 1 q4wk (four weeks = one treatment cycle).

Dose will be rounded to the first decimal.

Patients previously treated with PLD will be assigned to receive topotecan if they are randomized to the control arm.

- **Topotecan starting dose and schedule:**

- 1.50 mg/m² daily on Days 1-5 q3wk (three weeks = one treatment cycle) for patients with calculated CrCL \geq 60 ml/min.
- 1.25 mg/m² daily on Days 1-5 q3wk for patients with calculated CrCL between 40 and 59 ml/min.
- 0.75 mg/m² daily on Days 1-5 q3wk for patients with calculated CrCL between 30 and 39 ml/min.

Dose will be rounded to the first decimal.

Skipped doses of topotecan will not be replaced.

Patients previously treated with topotecan will be assigned to receive PLD if they are randomized to the control arm.

However, if the number of patients randomized to either PLD or topotecan reaches 60% of the total number of patients expected in the control arm (i.e. 126 patients), then the treatment of choice in the control arm will be restricted to the less frequent control drug until the end of accrual (see Section [5.6](#)).

The dose for all three agents (PM01183, PLD or topotecan) will be capped at a body surface area (BSA) of 2.0 m² in those patients who have a greater BSA. BSA will be calculated according to the standard nomogram used at each center.

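### Three timing gaps in the PRO plan: SAP tables set at weeks without a questionnaire, a baseline that can follow known allocation, and time since dose that can differ between PM01183 and PLD

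*Protocol*

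**What the plan says.** **Schedule.** The protocol synopsis (Patient-reported outcomes) says that "PRO will be assessed every eight weeks from randomization and while on treatment to determine if efficacy and side effects" are matched by changes in quality of life. Protocol 5.7, Table 6 gives the timing as "Every eight weeks from randomization". Its footnote allows "a 1-week window for tumor assessments as per RECIST v.1.1, tumor marker evaluation and patient-reported outcomes" and applies one schedule whatever the treatment. Neither place says whether a questionnaire due on an infusion day is completed before or after the infusion.

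**Cycles.** Protocol 6.3 gives PM01183 "on Day 1 q3wk (three weeks = one treatment cycle") and PLD "on Day 1 q4wk (four weeks = one treatment cycle"). Topotecan is given on Days 1-5 of a three-week cycle.

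**Baseline.** Protocol 5.4, Table 5 times the baseline questionnaires "Within 7 days prior to first infusion", with a 1-day allowance. The Schedule of Assessments agrees, and protocol 5.2 runs the pre-treatment period up to the first infusion. The trial is open-label (protocol Section 3).

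**Analysis.** SAP 8.4 repeats the eight-week interval, and SAP 8.8 says protocol windows will be respected. The PRO tables in SAP 12.8 nevertheless show Week 6 (Tables 12.8.1-12.8.3) and Week 12 (Tables 12.8.2-12.8.3). They compare PM01183 with pooled control, with PLD alone and with topotecan alone. The mixed model in SAP 12.8 contains treatment, days after baseline and their interaction, and no term for time since dose.

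**The concern.** The PRO objective asks whether efficacy and side effects show up in quality of life, so it matters when each questionnaire is completed. The three points are separate and none causes another.

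- **Table weeks.** If windows are respected, the Week 6 and Week 12 rows have no scheduled data. The programmer must then either leave them empty or choose a mapping after the data are seen.
- **Baseline.** A patient who knows which drug she will receive may answer differently. Tables 12.8.2 and 12.8.3 are built on change from baseline, so a reaction that differs by arm enters each of those comparisons.
- **Time since dose.** A common calendar laid over cycles of different length can catch the drugs at different points after dosing. A difference between PM01183 and PLD could then mix drug effect with days since dose, and the SAP has no way to see it.

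**Working it through.** The documents state no time-since-dose figure to reproduce, so the check is calendar arithmetic and a comparison of sections.

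**(a) Table weeks.** Scheduled weeks are 8, 16, 24 and so on. The 1-week window, read as plus or minus 7 days, gives weeks 7-9, 15-17 and 23-25.
- Week 6: distance to week 8 = 2 weeks, outside 7-9.
- Week 12: distance to week 8 or week 16 = 4 weeks, outside both windows.

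**(b) Baseline.** Randomisation is meant to be close to the first dose (protocol 5.6), but it still precedes it. A questionnaire completed between the two satisfies Table 5. If knowing the allocation shifts the baseline score by d_A in Arm A and d_B in Arm B, the between-arm difference in change shifts by -(d_A - d_B). The documents give no value for either.

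**(c) Time since dose.** Assume the first dose is on the day of randomisation and there are no delays. Days since the last Day 1 = visit day modulo cycle length (21 or 28). A visit on a dosing day counts as pre-infusion, that is, as a full cycle.

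| Visit | PM01183, topotecan | PLD | Gap |
|---|---|---|---|
| Week 8 (day 56) | 56 mod 21 = 14 | 56 mod 28 = 0, so 28 | 14 |
| Week 16 (day 112) | 112 mod 21 = 7 | 112 mod 28 = 0, so 28 | 21 |
| Week 24 (day 168) | 168 mod 21 = 0, so 21 | 168 mod 28 = 0, so 28 | 7 |

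If completed after the infusion, the PLD value is 0 instead of 28 at each visit. Counted from topotecan's Day 5, its values are 10, 3 and 17 days. The pattern repeats every 24 weeks.

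*Pooled control.* Either control drug is capped at 126 of 210, so PLD is 84-126 patients, or 40-60%, at full accrual. The excess over PM01183 is the share times the gap: 5.6-8.4 days at week 8, 8.4-12.6 at week 16 and 2.8-4.2 at week 24.

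*Window.* With visits spread evenly over plus or minus 7 days, week 8 spans 7-21 days for three-week drugs and 1-28 for PLD (means 14.0 and 14.9). Week 16 spans 1-21 and 1-28 (means 8.4 and 14.9).

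*Delays* (up to two weeks are permitted, protocol 6.5). One 7-day delay in each arm gives 7 versus 21 days at week 8 and 21 versus 21 at week 16. One 14-day delay in each arm gives 21 versus 14 at week 8, which reverses the order.

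*Who is seen.* Using protocol 8.1 (exponential, control median 3.5 months, HR 0.7), control progression-free = 0.5^(t/3.5) and Arm A = that value to the power 0.7. With week 8 at 1.84 months, weeks 8, 16 and 24 give about 69%, 48% and 34% in control and 77%, 60% and 47% in Arm A. These are approximate upper limits for being on treatment. The two visits with the larger gaps are therefore the ones with most patients.

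*In points.* Suppose a 0-100 scale is k points worse one to two weeks after dosing than just before the next dose. On nominal dates the PM01183-versus-PLD difference at weeks 8 and 16 shifts by k, and the pooled one by 0.4k to 0.6k. For k = 0, 5 and 10 the pooled shift is 0, 2-3 and 4-6 points. The documents give no k, and its sign could be opposite.

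**The case against.** **The calendar is symmetric by design.** Questionnaires share the eight-weekly dates of tumor assessment and CA-125, whatever the drug. This stands. It also means a reader should not infer that nothing else happens on those days.

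**Confounding is not shown.** The window, permitted delays and missing pre-infusion rule spread the actual timing, and evenly spread visits nearly balance week 8. This stands too, and it rules out saying that the comparison *is* confounded. It does not show balance: at week 16 the means still differ, 8.4 versus 14.9 days, and nothing planned would reveal what happened.

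**PLD patients need not be recovered.** One might infer from the re-treatment criteria that PLD is always measured after recovery. Those criteria govern the infusion. A patient held back for hand-foot syndrome can still complete her questionnaire on the due date.

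**The nadir is a laboratory finding.** Protocol 1.2.1.3 reports a second-week nadir for PM01183 in its account of hematological toxicity. No section links quality-of-life scores to cycle day.

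**The table weeks are only shells.** They are followed by ellipses, Table 12.8.1 shows Week 6 but not Week 12, and the mixed model uses days. All true, but the t-test and responder tables are still laid out by week.

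**Screening ends at randomisation.** Protocol 7.4.2 describes screening that way when setting SAE reporting, and Table 5 is headed as screening. That suggests the intent, but the timing written in Table 5 and protocol 5.2 runs to the first infusion.

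**Conclusion.** Three limited points hold.

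- (a) The SAP table weeks contradict the eight-week schedule. This rests on the documents alone.
- (b) Baseline PRO can follow known allocation. The plan permits this but does not require it; the size of any bias is unknown, and between arms only a differential reaction matters.
- (c) At nominal weeks 8 and 16, time since Day 1 differs by 14 and 21 days between PM01183 and PLD. That comparison, and the 40-60% of pooled control on PLD, can be confounded. PM01183 versus topotecan is largely unaffected because both have three-week cycles, and week 24 falls on Day 1 for every drug. The end-of-treatment questionnaire is tied to about 30 days after the last infusion in all arms.

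The day counts in (c) assume first dosing at randomisation, no delay and pre-infusion completion. A reader might go on to infer a known bias of 5-10 points. The documents do not support that: the figure is only an assumed range, and zero or a reversed sign is equally compatible with them. PRO is a secondary endpoint, and the primary PFS analysis does not depend on any of this.

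**What to change.** 1. **SAP 12.8.** Relabel Tables 12.8.1-12.8.3 to Weeks 8, 16, 24 and so on, each with the protocol's 1-week window. Cost: table headings.
2. **Protocol Table 5 and Schedule of Assessments.** Require the baseline questionnaires before randomisation, keeping the present limit relative to first infusion. SAP 8.1 takes the last value up to the first treatment day when there are several, so state that baseline PRO is the last one before randomisation. Cost: one sentence in each place; the baseline may lie a few days further from the first dose.
3. **Protocol Table 6.** State that a questionnaire falling on an infusion day is completed before the infusion. Listing 13.1.50 shows a date but no time of day, so the order cannot be recovered later.
4. **SAP 8.4 and 12.8.** Derive days since last dose from the questionnaire and administration dates already collected, report them by visit, arm and control drug, and add a sensitivity analysis using them. Cost: one derived variable and one extra model. The limitation should be stated: if patients keep to nominal dates there is little overlap (7 versus 28 days at week 16), so adjustment would lean on the model, and delays are themselves post-randomisation events.

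Keep the common eight-week calendar. Moving three-week drugs to their nearest Day 1 (week 9, then 15) while PLD stays at weeks 8 and 16 looks attractive, and each such date is inside the nominal window. But week 9 can fall after the week-8 scan. Patients who stop at progression could then be lost selectively by drug, and everyone would be measured late in the cycle, which works against detecting side effects. It would still leave 21 versus 28 days.

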1. INTRODUCTION

1.1 OVARIAN CANCER

Epithelial ovarian carcinoma is one of the most common gynecological malignancies and has the highest rate of cancer-related mortality among gynecological cancers in developed countries. It is the seventh most frequent cause of cancer death in women worldwide [1] and the fifth in the USA [2]. Half of the cases occur in women over 65 years.

Most ovarian cancers are sporadic; hereditary syndromes account for 10-15% of cases. Approximately 90% of hereditary ovarian cancer cases are associated with mutations in BRCA1 (chromosome 17) and BRCA2 (chromosome 13). Women with mutations in BRCA1 have a 40-50% chance of developing ovarian cancer and those with BRCA2 mutations have a 15-25% risk [3-5]. Hereditary non-polyposis colorectal cancer (HNPCC, Lynch II syndrome) carries an ovarian cancer risk of 12% [6]. Hereditary syndromes have to be distinguished from familiar syndromes. Women who have a single family member with epithelial ovarian cancer have a 4-5% risk, and those with two affected relatives have a 7% risk of developing ovarian cancer [7].

Due to the absence of specific clinical symptoms and the lack of standard screening tests for early diagnosis, nearly 75% of the patients have advanced stage at diagnosis. The International Federation of Gynecology and Obstetrics (FIGO) classification is the most extended staging system used. Survival rates at 5 years do correlate with the FIGO stage at diagnosis: 5-year survival exceeds 90% in early stages (IA, IB), but decreases to 40% and 20% in advanced stages (III and IV, respectively) [8].

Maximal surgical cytoreduction, followed by platinum-based combination chemotherapy are the standard of care for patients with advanced ovarian cancer. Combinations of platinum salts (carboplatin or cisplatin) with paclitaxel are highly active and induce objective response in 75% of patients, including nearly 40% of clinical complete responses [9, 10]. Complete response (CR) rate is higher in patients with early FIGO stage at diagnosis and in those with optimal debulking surgery. Platinum/paclitaxel combinations have also shown a significant improvement in progression-free survival (PFS) (18 vs. 13 months) and overall survival (OS) (38 vs. 24 months) compared to platinum combinations with older alkylant agents (cyclophosphamide), and therefore have become the standard frontline chemotherapy for advanced disease.

Despite this highly effective treatment, three quarters of the patients relapse and die due to progressive disease. The goal of treatment of relapsed ovarian cancer is palliative, as there is no realistic chance of curing patients whose disease has relapsed. On this basis, quality of life, prolongation of survival and control of cancer related symptoms are the primary goals of treatment of recurrent disease [11].

Given its therapeutic and prognostic relevance [12, 13], recurrent ovarian cancer is usually classified according to the length of platinum-free interval (PFI), defined as the time between completion of the last platinum-containing regimen and the subsequent relapse or progression. Ovarian cancer with a PFI longer than six months (i.e., the time between completion of the last platinum-containing chemotherapy and the date of relapse is longer than 6 months), is classified as platinum-sensitive. Patients with platinum-sensitive ovarian cancer have high likelihood of responding to a subsequent platinum-based chemotherapy and generally respond to non-platinum-based therapies as well. They have an overall better survival prognosis. Several therapeutic options are

available for platinum-sensitive disease, including platinum combinations with paclitaxel, gemcitabine or pegylated liposomal doxorubicin (PLD) [14-16], and non-platinum agents either alone or in combination (e.g., trabectedin plus PLD) [17-23].

In contrast, patients with platinum-resistant disease (PFI: 1-6 months) and those progressing or failing to achieve a response to a platinum-containing combination (platinum-refractory; PFI < 1 month) are less likely to respond to any subsequent therapy and have the worst prognosis in survival expectancy. Therapeutic options for these patients are very limited, and response rates rarely exceed 15%. Combination chemotherapy has not proven superior to monotherapy and it is usually more toxic.

The preferred chemotherapy for patients with platinum-resistant ovarian cancer is a single non-platinum agent. None of the approved chemotherapy agents (topotecan, PLD or paclitaxel) has been proved superior in OS in platinum-resistant ovarian cancer patients. Indeed, to date no approval of any available chemotherapies was granted on the basis of results in this specific disease setting; rather, results available for the relapsed ovarian cancer population in general were extrapolated. Response rates with single agents in platinum resistant disease are usually within the 10-15% range; PFS ranges 3 to 4 months, and OS is usually below one year with some exceptions (Table 1). Combination of chemotherapy with bevacizumab has not shown a statistically significant OS advantage over chemotherapy alone.

Table 1. Efficacy results of non-platinum chemotherapy in clinical trials conducted in platinum-resistant/platinum-refractory ovarian cancer patients.

Study (reference)	No of patients *	Treatment arms (n)	Refractory (%)	ORR (%)	PFS (mo)	OS (mo)
Ten Bokkel Huinink et al. (1997) [24]	119	Topotecan (60)	57	13.3	NA	NA
		Paclitaxel (59)	56	6.7	NA	NA
Gordon et al. (2001) [25]	254	Topotecan (124)	NA	6.5	3.4	10.3
		PLD (130)	NA	12.3	2.3	8.9
Gore et al. (2001) [26]	152	Oral topotecan (77)	52	8.0	NA	NA
		i.v. topotecan (75)	52	8.0	NA	NA
Mutch et al. (2007) [27]	195	Gemcitabine (99)	NA	6.1	3.6	Gem/PLD 12.7
		PLD (96)	NA	8.3	3.1	PLD/Gem 13.5
Vergote et al. (2009) [28]	461	Canfosfamide (231)	41	4.3	2.3	8.5
		PLD (130)	15	10.9	4.3	14.2
		Topotecan (87)				10.8
Vergote et al. (2010) [29]	125	Canfosfamide plus PLD (65)	20	12.3	5.6	11.8
		PLD (62)	13	8.3	3.7	7.8
Sehouli et al. (2011) [30]	194	Topotecan standard (97)	NA	19.0	4.4	9.3
		Topotecan weekly (97)	NA	9.0	3.0	9.6
Colombo et al. (2012) [31]	829	Patupilone (412)	20.1	15.5	3.7	13.2
		PLD (419)	18.8	7.9	3.7	12.7
Pujade-Lauraine et al. 2012 [32]	361	Chemotherapy ** (182)	Not allowed	12.6	3.4	13.3
		Chemotherapy** plus bevacizumab (179)		30.9	6.7	16.6
Witteveen et al. 2013 [33] (AURELIA trial)						

*Including both platinum-resistant and platinum-refractory ovarian cancer.

**Chemotherapy=topotecan (daily or weekly), weekly paclitaxel or PLD.

Gem, gemcitabine; mo, months; NA, data not available; ORR, overall response rate; OS, overall survival; PFS, progression-free survival; PLD, pegylated liposomal doxorubicin.

The treatment of patients with platinum-resistant ovarian cancer is usually chosen based on the individual safety profile, since all these agents show very similar and limited efficacy, and the therapy aim is mainly to delay disease progression and palliate symptoms. These patients are usually candidates for clinical trials testing new treatment options.

